2. STUDY SYNOPSIS

TITLE	Pharmacokinetics of Intramuscular Versus Subcutaneous Administration of Benzathine Penicillin G (Bicillin® L-A)
OBJECTIVES	
Primary Aim:
 
 To compare the pharmacokinetics, in particular, the rate of absorption of Bicillin® L-A administered by the subcutaneous route and the intramuscular route in healthy adults 
Secondary aims:
 
 To measure the pain experienced by participants administered Bicillin® L-A by the subcutaneous route compared to the intramuscular route To measure the frequency, types, and severity of adverse events related to Bicillin® L-A administered by the subcutaneous route compared to the intramuscular route
DESIGN	A single-blinded study in 2x2 crossover using two doses of Bicillin® L-A administered by the subcutaneous and intramuscular route with a 10-week wash-out period between doses. Serum penicillin levels and pain scores just prior to injection and at pre-determined intervals for six weeks following each injection will be collected. An ultrasound scan will be used to guide and confirm injection site and document location of medication bolus on injection day and local changes at injection sites at four weeks after injection.
OUTCOMES	
Primary outcome measure:
 
 The rate of absorption of Bicillin® L-A administered subcutaneously and intramuscularly 
Secondary measures:
 
 Time above the minimum inhibitory concentration (0.02mg/mL) for Streptococcus pyogenes Pain scores associated with receiving Bicillin® L-A administered subcutaneously and intramuscularly Type, number, and severity of adverse events following subcutaneous compared to intramuscular administration of Bicillin® L-A Type and number of ultrasound-detected local changes following subcutaneous compared to intramuscular administration of Bicillin® L-A
STUDY DURATION	Six months (each participant will be in the study for 18 weeks)

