6.4.2. Pain of BPG IM injections

The pain associated with IM BPG injection is frequently cited as a reason for lack of compliance to SP.^{28,34} Whilst the exact mechanism behind the pain is poorly understood, studies have shown that patients who receive BPG injections do not 'get used to' injections, as some believe.^{5,28,29} There have been several interventions that have shown some efficacy in reducing the pain in children and adolescents receiving BPG injections. Studies have demonstrated a reduction in pain scores with the co-administration of lignocaine. Powdered BPG can be reconstituted with lignocaine in place of sterile water. The resultant injection has significantly reduced pain with no significant alteration in pharmacokinetics.³⁰ New Zealand Ministry of Health recommends the addition of lignocaine to Bicillin® L-A to reduce injection pain.³⁵ This practice is not endorsed by the manufacturer due to potential loss of sterility and is not routinely used in Australia. Use of the Buzzy®, and with addition of lignocaine to Bicillin® L-A, have been shown to reduce pain for up to 12 hours in populations of

children, however, the efficacy decreases with age. Additionally, application of pressure and temperature packs are two methods that have shown significant reduction in pain scores with BPG injections.^{28,30,36} These interventions do not make the procedure painless, however, they do significantly reduce the pain experienced by children.

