9.1.9. Sampling schedule

It is expected the study will occur over an 18-week period. There will be a maximum of 26 DBS samples taken from each participant through the study period. Additionally, baseline blood tests will be performed in the screening period. A serum sample will be taken at 12 hours and at 14 days post-injection to compare penicillin levels to DBS. Participants will be recruited in month 1; after consent and screening tests, they will then be randomised to receive IM or SC Bicillin® L-A in month 1 as per the schedule (a-e):

(a) Enrolment and screening (2 weeks).

Potential participants will be screened according to the clinical criteria as described in section 6.5. They will then undergo the consent process, the required screening including history, and examination and screening blood tests as outlined in section 9.1.4-9.1.5. If any significant abnormalities are found on screening, they will be referred as clinically appropriate for further testing via their general practitioner and exit the study. Those who fulfil all inclusion and no exclusion criteria will then be blinded and randomised to Group A or Group B (see Table 3).

(b) Administration period 1 (6 weeks).

Participants will be randomised to either the SC or IM administration of Bicillin® L-A in the upper outer quadrant of buttock at day zero. The IMP (Bicillin® L-A) will be prepared as per the manufacturer's instruction in the product information sheet. Injection will occur with a 20G needle of appropriate length. The route of administration will be confirmed via real-time ultrasound imaging; the procedure is outlined in section 10.6. DBS samples will be taken at: baseline, then t=2,

6, 12, and 24 hours, followed by day 2, 3, 5, 7, 14, 21, 28, and 42. There is some flexibility in sampling times as demonstrated in Table 4 below. Pain scoring will be taken routinely at: baseline, t=2, 6, 12, 24, 48, and 72 hours, then at day 5, 7, 14, 21, 28, and 42 if injection-associated pain is recorded at the prior visit. Venesection will be conducted at baseline, 12 hours after the dose of BPG and at day 14 for baseline biochemical and haematological profile and to demonstrate concordance between plasma and DBS penicillin concentrations.

(c) Washout period (4 weeks).

Participants will undergo a washout period of at least 28 days after administration period 1.

(d) Administration period 2 (6 weeks).

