After the washout period, participants will receive alternate administration of IM or SC Bicillin® L-A, dependent on the route of administration in period 1. The IMP (Bicillin® L-A) will be prepared as per the manufacturer’s instruction in the product information sheet. Injection will occur with the 20G needle supplied as part of the Bicillin® L-A product. The route of administration will be confirmed via real-time ultrasound imaging. The procedure is outlined in section 10.6. DBS samples will be taken at: baseline, t=2, 6, 12, and 24 hours, followed by day 2, 3, 5, 7, 14, 21, 28, and 42. There is some flexibility in sampling times as demonstrated in Table 4 below. Pain scoring will be taken routinely at: baseline, t=2, 6, 12, 24, 48, and 72 hours, then at day 5, 7, 14, 21, 28, and 42 if injection-associated pain is recorded at the prior visit. Venesection will be conducted on days 0 and 14 to verify the DBS levels.

(e) Post-sampling telephone follow-up (2 weeks).

Participants will be followed up after a 14-day period by telephone to confirm no persisting AEs; if present, they will be formally reviewed by a study team member.

Table 4: Sampling schedule for both administration periods 1 & 2

T: hrs (days)	0	2	6	12	24 (1)	48 (2)	72 (3)	120 (5)	168 (7)	336 (14)	504 (21)	672 (28)	1008 (42)
DBS	Y	Y	Y	Y	Y	Y	Y	Y	Y	Y	Y	Y	Y
Sampling window [‡]	-	±5 min	±15 mins	±30 mins	±4 hours	±8 hours	±12 hours	±1 day	±1 day	±2 days	±2 days	±2 days	±2 days
Pain score	Y	Y	Y	Y	Y	Y	Y	Y*	Y*	Y*	Y*	Y*	Y*
Venesection	-	-	-	Y	-	-	-	-	-	Y	-	-	-
USS	Y	-	-	-	-	-	-	-	-	-	-	Y	-

DBS = dried blood spot; Y = yes; * = possible measurement; USS = ultrasound scan of injection site (see appendix 8)
; [‡] = time in minutes/hours/days following Bicillin® L-A injection.

A study sampling schedule from screening through to follow up phone call is included as Appendix 7 for ease of reference.

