13. The time of completion of the injection will be documented, and sampling using DBS and NRS post-injection carried out as scheduled using the end of injection time as the reference point.
14. The participant will be monitored for AEs in the clinical trial facility for 12 hours post-injection.
15. Participant pain scores will be recorded at the time intervals specified above.

16. The participant will be discharged and instructed to follow up at the appropriate times.

Subcutaneous injection

1. On morning of injection, the Bicillin® L-A 1016.6mg or 1.2MIU (2.3ml) and supplied needle will be removed from fridge at least 3 hours prior to injection time to allow suspension to reach room temperature. The syringe will later be further warmed by rolling the syringe between palms prior to injection.
2. The syringe will be placed in a clean field.
3. The participant will have consent checked and placed in prone position. Participants will nominate a buttock for the first administration period and asked to expose the buttock area. In second administration period, the opposite buttock will be used.
4. The injection will be undertaken in the clinical suite screened for privacy, with access to medical resuscitation equipment; adrenaline will be available. The injection will be performed by a suitably qualified investigator who has undertaken the online training module on BPG injection developed by Pfizer with RHD Australia (<https://www.rhdaustralia.org.au/administering-bicillin>).
5. A screen will be set up to prevent participant observation of the US monitor and injection site. Landmarks will be palpated to estimate the dorso-gluteal injection site.
6. US will be used to confirm the injection site and determine the thickness of SC tissue. Distance from skin to the gluteal muscle will be measured.
7. Skin will be cleaned and prepped using alcohol swab.
8. Using sterile technique, the needle will be attached to the syringe.
9. Manual pressure will be applied over the site for 30 seconds prior to injection.

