20.7. Appendix 7- Study Schedule of Assessments

	Screen	Period 1 and Period 2												Washout Period	Follow-up Period		
	2 weeks	Day 0					Day 1	Day 2	Day 3	Day 5	Day 7	Day 14	Day 21	Day 28	Day 42	4 weeks	14 Days after Completing Period 2
Event ▼	Study Hour ►	Pre-dose	0 h	2	6	12	24	48	72								
Informed Consent	X																
Inclusion/Exclusion Criteria	X	X															
Demographics																	
Medical History	X																
Height	X																
Physical Exam (incl. weight)	X																
Vital Signs	X	X		X	X	X											
Clinical Laboratory Tests	X	X															
HIV, Hepatitis B/C Testing	X																
Urine Drug / Alcohol Breath Test	X	X															
Dried Blood Sampling PK Sample		X		X	X	X	X	X	X	X	X	X	X	X	X		
PK Blood Sample (from a vein)						X						X					
Pain Score			X	X	X	X	X	X	X ²	X ²	X ²	X ²	X ²	X ²	X ²		
Monitoring of Skin Irritation							X	X	X ²	X ²	X ²	X ²	X ²	X ²	X ²		
Ultrasound Scan of Injection Site			X										X				
Study Medication Administration			X														
Adverse Events		←															→
Record Current Medications	←																→
In Clinic Confinement		←				→											
Outpatient Visit	X						X	X	X	X	X	X	X	X	X		
Telephone Call Follow-up																	X

¹ Participants should be resting in a supine position for at least 5 minutes prior to and during the measurement of vital signs. When vital signs are scheduled at the same time as blood draws, the vital signs will take priority. Additional vital signs may be performed as clinically indicated.

² Assessments performed only if pain or irritation was recorded at the previous visit.

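### The time-zero pain score is defined inconsistently, and no reading of the schedule gives both a pre-injection and an end-of-injection score

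*Protocol*

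**What the plan says.** The synopsis (Design) says "Serum penicillin levels and pain scores just prior to injection and at pre-determined intervals for six weeks following each injection will be collected". Section 9.1.9(b) for period 1 and 9.1.9(d) for period 2 both read "Pain scoring will be taken routinely at: baseline, t=2, 6, 12, 24, 48, and 72 hours", followed by days 5 to 42 only if pain was present at the prior visit.

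Section 10.6 describes the injection, given over 3 minutes by either route. Step 13 has "sampling using DBS and NRS post-injection carried out as scheduled using the end of injection time as the reference point". Step 15 adds no time of its own: "Participant pain scores will be recorded at the time intervals specified above".

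Table 4, titled "Table 4: Sampling schedule for both administration periods 1 & 2", has one column headed 0 with a pain score marked in it; the next column is 2 hours. Appendix 7 has separate Pre-dose and 0 h columns. The baseline dried blood spot sits under Pre-dose. The first pain score sits under 0 h, with study drug administration, and the pain row is blank under Pre-dose.

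Pain by route is a secondary objective (5.2) and a secondary endpoint (7.4(a)). Section 5.3 lists a possible IM/SC difference in injection-related pain among the questions the trial should inform.

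**The concern.** The time-zero score has two possible meanings, and they are different measurements. A score before the needle is a baseline, expected to be near zero. A score at the end of the injection measures how much the injection hurt. The protocol does not say consistently which one is collected. Its main text points to the first, and the next score is then at 2 hours.

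The background gives acute pain weight: "The pain associated with IM BPG injection is frequently cited as a reason for lack of compliance to SP", and 6.1.4 names fear of the injection as well as its pain. The gap may also not be neutral between routes. Section 6.2 reports from an early trial that accidental SC placement gave more prolonged discomfort, of unquantified severity. A schedule that starts at 2 hours could pick up that possible drawback of SC while missing any difference between routes during the injection.

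An analysis plan cannot repair this, because it cannot recover a score that was never taken.

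**Working it through.** **1. The protocol's own pain calculation (12.2).** Inputs: difference 2 points, SD 1.7, correlation 0.3, paired t-test, alpha 0.05 (12.3; taken as two-sided).

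SD of the paired difference = 1.7 × √(2 × (1 − 0.3)) = 2.011. Noncentrality at n = 15 = (2 / 2.011) × √15 = 3.85, on 14 degrees of freedom.

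| n | Stated power | Recomputed |
|---|---|---|
| 15 | 94.6% | 94.7% |
| 12 | 87.9% | 87.9% |
| 10 | 79.8% | 79.9% |

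The calculation is right on its inputs. It does not name the time point at which the 2-point difference is expected.

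**2. The schedules side by side.**

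| Source | Before injection | During or just after | Next score |
|---|---|---|---|
| Synopsis | yes | none named | pre-set intervals |
| 9.1.9(b), (d) | yes (baseline) | none | 2 h |
| 10.6 | none of its own | none of its own | refers back to the schedule |
| Table 4 | one mark at 0, before or after not stated | (same mark) | 2 h |
| Appendix 7 | blank | one mark at 0 h, dosing column | 2 h |

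Column 0 of Table 4 cannot decide the matter. It also holds the baseline blood spot, taken before dosing, and the ultrasound, which by the synopsis both guides the injection and documents the bolus afterwards.

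**3. Is the 0 h score additional to the baseline?** Count the scores per period.

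- 9.1.9: baseline + 6 (2 to 72 h) + 6 conditional (days 5, 7, 14, 21, 28, 42) = 13.
- Table 4: 7 routine + 6 conditional = 13.
- Appendix 7: 6 unconditional (0 to 48 h) + 7 conditional (72 h to day 42) = 13.

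All three list 13. A schedule with both a baseline and an end-of-injection score would need 14. The 0 h mark is therefore the same single score placed elsewhere.

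**4. Length of the gap under the main text.** Post-injection times run from the end of injection, the injection takes 3 minutes, and the 2-hour window is ±5 minutes. From the start of injecting to the first score is 3 + 120 = 123 minutes, or 118 to 128 minutes with the window. The participant is in the clinic throughout, since 10.6 keeps him there for 12 hours.

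**5. A related mismatch.** The 72-hour score is routine in 9.1.9 and Table 4. In Appendix 7 it carries the footnote "Assessments performed only if pain or irritation was recorded at the previous visit".

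**The case against.** The strongest reply is that an injection score does exist. Appendix 7 separates Pre-dose from 0 h and puts pain at 0 h; read with the end-of-injection reference in 10.6 step 13, that can be taken as a score when the injection finishes. This stands as a possible reading, so it would be too strong to say that the protocol schedules no injection score at all. But nothing defines 0 h that way, the reading contradicts the synopsis and 9.1.9, and it leaves no pre-dose score.

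A second reply is that the Appendix 7 argument rests on one cell of a table whose columns may not be reliable: its second ultrasound falls under day 21, while Table 4 and the synopsis put it at four weeks. That caution is fair. Other rows do line up with the body text, though: venous samples at 12 hours and day 14, and skin inspection on days 1 and 2. If the cell were disregarded, the main text would stand alone, with no score between baseline and 2 hours.

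A reader might go further and infer that the trial cannot say which injection hurts less. The protocol does not support that. The endpoint in 7.4(a) is not limited to pain during the injection, 9.1.6 follows pain until it returns to zero, and 6.4.2 treats pain over the following 12 hours as relevant. Scores from 2 to 72 hours still compare the routes on later injection-related pain.

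A reader might also infer that the power in 12.2 collapses because pain will have faded by 2 hours. The protocol gives no time course of pain, and the answer turns on one further assumption. For a 30% difference at a comparator score of 3 with n = 15, power is 36% if the SD stays at 1.7 but 90% if the SD falls in proportion to the mean, the same as at a score of 6. No figure for lost power can be drawn from this.

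**Conclusion.** The point holds as an inconsistency with a practical consequence. The time-zero pain score is before the injection in the synopsis and 9.1.9, in the dosing column in Appendix 7, and undetermined in Table 4. No reading yields both a baseline and an end-of-injection score. Followed as written, the main text collects 0 of its 13 scores per period (7 routine, 6 conditional) between the start of injecting and about 2 hours later, so acute injection pain goes unmeasured.

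This rests on the synopsis wording as the meaning of baseline and on the Appendix 7 columns as they appear. It assumes nothing about how fast pain fades. Pain is a secondary endpoint and the primary pharmacokinetic comparison is unaffected, but the correction is cheap and the missing score cannot be recovered later.

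**What to change.** Reconcile the synopsis, 9.1.9(b) and (d), Table 4 and Appendix 7. In each, schedule:

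- an NRS score before dosing;
- a separate NRS score at the end of injection, asking about pain during the injection;
- the scores from 2 hours onward as already planned.

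Split column 0 of Table 4 into pre-dose and end of injection so that it matches Appendix 7. State in 12.2 which time point the 2-point pain calculation refers to. In the same amendment, settle whether the 72-hour score is routine or conditional.

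The cost is one extra question and one CRF field per period. That is at most 15 × 2 = 30 additional scores over the whole trial, from participants who are already in the clinic.

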6.2. Pharmacokinetics of BPG

BPG has favourable characteristics which make it ideal for slow-growing organisms and for SP. Its long serum half-life compared to other forms of penicillin, allows for the serum levels to remain above minimum inhibitory concentration (MIC) for several weeks. This unique characteristic of BPG is due to the slowed absorption from the IM depot formed on injection. Initial studies in the 1950s showed the superiority of BPG when compared to sulfadiazine and oral penicillin. Subsequent studies went on to establish the PK profile and show superiority of BPG for SP.¹¹

Stollerman et al. in 1955 compared BPG and oral penicillin efficacy in 329 patients with ARF or RHD; 145 patients received BPG 1.2MIU via 4-weekly intramuscular injection, 111 patients received oral penicillin V 100,000 units twice daily, and 73 received oral sulfadiazine 1gm daily. There were 0, 2 and 5 recurrences respectively, of ARF through the equivalent 242, 170, 130 patient years, respectively. They did note that on some occurrences when inadvertently given subcutaneously, BPG had a longer duration of discomfort, but they did not quantify the severity. Compared to healthy controls who had carriage rates of GAS of 19.3%, the intervention groups had lower rates of GAS: 1.4%, 13.1% and 10.7% respectively for BPG, oral penicillin, and sulfadiazine respectively.¹¹

The ability to detect serum penicillin levels four weeks after administration above the in-vitro MIC, and demonstrated clinical superiority have resulted in BPG being the preferred agent for SP. Whilst the PK profile of BPG has been studied extensively, there has been increasing evidence to suggest that current dosing regimens are insufficient.^{9,31,32} During the 1990s, evidence emerged of lower than expected plasma drug levels after IM injection. A case was made for revising the dosing of BPG by Currie et al. 1994, who compared the protective plasma concentration of 1.2MIU, 1.8MIU, and 2.4MIU in adults. At 3 weeks, 50%, 73%, and 100% respectively had adequate penicillin levels. Only 24% (1.2MIU), 39% (1.8MIU), and 56% (2.4MIU) had protective levels at four weeks.¹⁰

It was noted that there were some individuals who had significantly different PK profiles and the authors postulated that this could be due to inadvertent adipose administration, but were unable to demonstrate this in their cohort.¹⁰

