9.1.7. Monitoring of skin irritation

The participant will be questioned regarding symptoms of pain, character, itchiness, pallor or erythema bleeding, and heat. Participants will be inspected by a study team member for evidence of skin erythema at day 1 and 2, with continued visual inspection if there was presence of pain or irritation as reported by the participant (days 4, 7, 14, 21, 28) until resolution. Area of irritation or erythema if present will be measured in length and width.

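### Late pain scores and skin checks are taken only after a positive prior visit, so new or returning symptoms get no scheduled grading, and the schedules disagree on the rule

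*Protocol*

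**What the plan says.** For both administration periods, section 9.1.9 states "Pain scoring will be taken routinely at: baseline, t=2, 6, 12, 24, 48, and 72 hours", and takes the scores on days 5, 7, 14, 21, 28 and 42 only "if injection-associated pain is recorded at the prior visit". Table 4 stars the same six late times as possible measurements. Section 9.1.6 adds that pain, if present, is followed until it returns to zero. It gives no rule for restarting.

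For the skin, section 9.1.7 has everyone inspected on days 1 and 2, "with continued visual inspection if there was presence of pain or irritation as reported by the participant", and lists days 4, 7, 14, 21 and 28. In Appendix 7, footnote 2 is attached to both the pain row and the skin row: "Assessments performed only if pain or irritation was recorded at the previous visit".

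The synopsis, in contrast, says that "pain scores just prior to injection and at pre-determined intervals for six weeks following each injection will be collected".

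Pain scores by route are a secondary endpoint (section 7.4), and the secondary hypothesis is that tolerability by the subcutaneous (SC) route is at least comparable with the intramuscular (IM) route (section 7.2).

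**The concern.** Whether a late pain score exists depends on the value of the score before it. Once a participant has a pain-free visit, the scheduled 0–10 question is not asked again in that period, and under Appendix 7 a clear visit also ends skin checks. He nevertheless attends in person on every later day for dried blood spot sampling. A single zero is enough, including one given while using the occasional paracetamol or ibuprofen that section 8.4 permits.

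The product is a depot absorbed over weeks, so a quiet site at 72 hours does not establish a quiet site later. What is at stake is the pain-score endpoint and the measured skin reactions. A conclusion that the routes are comparable is weaker if the schedule cannot register new or returning pain after a zero.

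Separately, the passages that set the rule do not agree, so staff cannot follow all of them.

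**Working it through.** **The plan's own figure.** Section 12.2 gives 94.6% power for the paired pain comparison at n = 15 (difference 2 points, SD 1.7, correlation 0.3). SD of the difference = 1.7 × √(2 × (1 − 0.3)) = 2.01; noncentrality = 2 / 2.01 × √15 = 3.85. A two-sided paired t-test at 5% gives 94.7%, so the figure reproduces. The calculation names no time point and the gate does not enter it, so this point leaves the stated power unchanged.

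**How many measurements are conditional, per period.**
- Pain, section 9.1.9 and Table 4: 13 times (0, 2, 6, 12, 24, 48, 72 h; days 5, 7, 14, 21, 28, 42). Conditional: 6.
- Pain, Appendix 7 as extracted: 13 marks, of which 7 carry footnote 2, starting at 72 h.
- Skin, section 9.1.7: 2 routine days and 5 conditional. Appendix 7: 2 routine and 7 conditional.
- A participant without pain at 72 h has no scheduled score for (42 − 3) / 42 = 39/42 = 93% of the six weeks. This is calendar time; it does not measure lost information.

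**What the rule records.** Assume that pain starts on the day shown, persists to day 42 and was absent before, and that pain counts as recorded at a visit only through a positive score. Applying the prior-visit rule in sequence to the 13 times gives these numbers of scheduled scores that record the pain:

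| Onset (day) | 9.1.9 / Table 4 | Appendix 7 | No condition |
|---|---|---|---|
| 1.5 | 8 | 8 | 8 |
| 2.5 | 7 | 0 | 7 |
| 3.5 | 0 | 0 | 6 |
| 6 | 0 | 0 | 5 |
| 10 | 0 | 0 | 4 |
| 20 | 0 | 0 | 3 |

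Pain that begins before the last routine score is followed in full. Pain that begins after it is not scored at all. Pain that returns after a zero behaves like new pain. The day 2.5 row shows what the disagreement over the 72-hour score is worth: seven scores or none.

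**The passages side by side.**

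| Item | Sections 9.1.7 and 9.1.9, Table 4 | Appendix 7 |
|---|---|---|
| 72 h pain score | routine | conditional (as extracted) |
| Skin-check days after day 2 | 4, 7, 14, 21, 28 | 3, 5, 7, 14, 21, 28, 42 |
| Trigger for later skin checks | pain or irritation that the participant reports | a finding recorded at the previous visit |

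**The case against.** The strongest reply is that late local reactions can still be found. Section 11.2 records all adverse events from enrolment to completion, whether staff observe them or participants report them. Participants are seen on days 3, 5, 7, 14, 21, 28 and 42. Every injection site is scanned at about four weeks regardless of symptoms, and a telephone call follows period 2. Section 9.1.7 opens with unconditional questioning about symptoms, although it names no days, and its trigger can be read to include a new complaint. All of this stands. A reader might infer that the trial misses delayed reactions altogether, and the documents do not support that. But none of these routes yields a scheduled pain score, and the ultrasound grades neither pain nor erythema.

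A reader might also infer that the rule favours SC. The documents do not support that either. The rule is the same for both routes. The background in section 6.2 says that "when inadvertently given subcutaneously, BPG had a longer duration of discomfort", which is persistence, and the rule follows persistent pain. The SC induration and granulomas in section 6.14.1 concern another depot drug, with no onset times.

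On the inconsistencies, some allowance is due. The day 5 visit has a window of ±1 day, so attendance on day 4 is possible. The synopsis is a summary that the body text refines more than it contradicts. The 72-hour conflict rests on an extracted table in which the late ultrasound mark falls under day 21, against day 28 in Table 4, so alignment is not certain. The count of 7 footnoted marks out of 13 does not depend on column position, but it should be checked against the source table.

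Finally, the statistical analysis plan may say how unscored visits are handled. It cannot recover a score that was never taken, and setting such visits to zero would assume what was not measured.

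**Conclusion.** The concern holds for scheduled graded measurement. Per period, 6 of 13 pain scores (7 of 13 in Appendix 7 as extracted) and the later skin checks in Appendix 7 depend on a positive finding at the prior visit. Symptoms that first appear or return after a clear visit get no scheduled grading, and the pain-score endpoint has missingness driven by its own earlier value. The size of any effect on the route comparison cannot be derived: it depends on how often late onset occurs and whether that differs by route, and the documents give neither. The direction of any bias is therefore unknown.

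The table of onset days rests on persistence to day 42 and on pain being recorded only through a positive score. If a complaint entered as an adverse event also counts, scoring could resume at the next visit, but the protocol does not say so. The primary endpoint and the stated pain power are unaffected. This is a low-cost improvement to a secondary endpoint, together with a schedule that needs to be made consistent.

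**What to change.** Delete the prior-visit condition in sections 9.1.6, 9.1.7 and 9.1.9 (both periods), in Table 4 and in Appendix 7 footnote 2. Keep the baseline, 2, 6 and 12 h pain scores. Record the pain score and inspect the site at every visit already scheduled (days 1, 2, 3, 5, 7, 14, 21, 28 and 42) for both routes. Align all five places to that one schedule, which also settles the 72-hour score, the skin-check days and the trigger.

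No new visits are needed. Relative to Table 4, the most this adds is 6 × 2 = 12 pain scores per participant, or 12 × 15 = 180 in the trial. Relative to Appendix 7, it is 7 × 2 = 14 pain scores and 14 skin inspections per participant. The cost is slightly longer visits and a change to the case report form and protocol wording.
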